### 982       **7.3 Reportable Device Issues**

983       All UADEs and ADEs as defined in section 7.2.1 will be reported on both a device issue form  
984       and AE form, except for skin reactions from CGM sensor placement or pump infusion set  
985       placement that do not require pharmacologic treatment.

986       Device complaints and device malfunctions will be reported except in the following  
987       circumstances. These occurrences are expected and will not be reported on a Device Issue Form  
988       assuming criteria for a UADE or ADE have not been met:

- 989       • CGM sensor needing replacement prior to labelled maximum use duration
- 990       • Infusion set needing replacement prior to labelled maximum use duration
- 991       • CGM tape adherence issues
- 992       • Pump infusion set insertion lasting fewer days than expected per manufacturer
- 993       • Battery lifespan deficiency due to inadequate charging or extensive wireless communication
- 994       • Intermittent device component disconnections/communication failures not requiring system  
995        replacement or workaround/resolution not specified in user guide/manual.
- 996       • Device issues clearly addressed in the user guide manual that do not require additional  
997        troubleshooting

### 998       **7.4 Timing of Event Reporting**

999       SAEs possibly related to a study device or study participation and UADEs must be reported by  
1000       the investigator to the Coordinating Center within 24 hours of the site becoming aware of the  
1001       event. This can occur via phone or email, or by completion of the online serious adverse event  
1002       form and device issue form if applicable. If the form is not initially completed, it should be  
1003       completed as soon as possible after there is sufficient information to evaluate the event. All other  
1004       reportable ADEs and other reportable AEs should be submitted by completion on the online form  
1005       within 7 days of the site becoming aware of the event.

1006 The Coordinating Center will notify all participating investigators of any adverse event that is  
1007 serious, related, and unexpected. Notification will be made within 10 working days after the  
1008 Coordinating Center becomes aware of the event.

1009 Each principal investigator is responsible for reporting serious study-related adverse events and  
1010 abiding by any other reporting requirements specific to his/her Institutional Review Board or  
1011 Ethics Committee. Where the JCHR IRB is the overseeing IRB, sites must report all serious,  
1012 related adverse events within seven calendar days.

1013 Upon receipt of a qualifying event, the Sponsor will investigate the event to determine if a  
1014 UADE is confirmed, and if indicated, report the results of the investigation to all overseeing  
1015 IRBs, and the FDA within 10 working days of the Sponsor becoming aware of the UADE per  
1016 21CFR 812.46(b) (2). The Sponsor in conjunction with the Medical Monitor must determine if  
1017 the UADE presents an unreasonable risk to participants. If so, the Sponsor must ensure that all  
1018 investigations, or parts of investigations presenting that risk, are terminated as soon as possible  
1019 but no later than 5 working days after the Sponsor makes this determination and no later than 15  
1020 working days after first receipt notice of the UADE. The investigator(s) may then be required to  
1021 provide approval or acknowledgment of receipt of that notification, and must submit to their  
1022 overseeing IRB as required.

1023 The investigators are also required to report, without unjustified delay, all device deficiencies  
1024 that could have led to a UADE, including device deficiencies, irrespective of whether an adverse  
1025 event occurred.

1026 Device malfunctions will be handled by the Sponsor or designee as described below. In the case  
1027 of a CGM transmitter or sensor device malfunction, information will be forwarded to Dexcom by  
1028 the site personnel, to be handled by their complaint management system.

## 1029 **7.5 Safety Oversight**

1030 The study Medical Monitor will review all adverse events and adverse device events that are  
1031 reported during the study. SAEs typically will be reviewed within 24 hours of reporting.  
1032 Other AEs typically will be reviewed on a weekly basis. Additionally, the Medical Monitor will  
1033 review compiled safety data at periodic intervals.

1034 The Clinical Study Director will be informed of all cases of severe hypoglycemia and DKA  
1035 and the Medical Monitor's assessment of relationship to the study device; and informed of all  
1036 reported device issues.

## 1037 **7.6 Stopping Criteria**

### 1038 **7.6.1 Participant Discontinuation of Study Device**

1039 In the case of an unanticipated system malfunction resulting in a severe hypoglycemia or DKA  
1040 event (or a malfunction that could have led to severe hypoglycemia or DKA), use of closed-loop  
1041 mode will be suspended while the problem is diagnosed. The UADE will be reported to the IRB  
1042 and FDA. After assessment of the problem and any correction, use of closed-loop mode will not  
1043 be restarted until approval is received from the IRB and FDA.

1044 In the absence of a device malfunction, a participant will be discontinued from the study if any of  
1045 the following occur:

1046     • The investigator believes it is unsafe for the participant to continue on the intervention. *This*  
1047     *could be due to the development of a new medical condition or worsening of an existing*  
1048     *condition; or participant behavior contrary to the indications for use of the device that*  
1049     *imposes on the participant's safety*

1050     • The participant requests that the treatment be stopped

1051     • Participant pregnancy

1052     • Two distinct episodes of DKA, HHS, or severe hypoglycemia as defined above, so only a  
1053     second event of any of these types may occur prior to stopping subject participation.

1054     Each DKA or severe hypoglycemia event will be reviewed by the Medical Monitor with respect  
1055     to determination of cause and whether the occurrence of the event can be attributed to use of the  
1056     study device.

1057     An additional requirement for continued study participation following a single DKA or severe  
1058     hypoglycemia event will be that (1) the site investigator believes that the event is explainable,  
1059     unlikely to recur, and that it is safe for the participant to continue to use the system and (2) the  
1060     Medical Monitor concurs. If the Medical Monitor determines that the occurrence of the event  
1061     indicates that it is not safe for the participant to continue to use the study system, the participant  
1062     will be discontinued from the study.

1063     Even if the study device system is discontinued, the participant will be encouraged to remain in  
1064     the study through the final study visit.

1065                   **7.6.2 Criteria for Suspending or Stopping Overall Study**

1066     In addition to the suspension of closed-loop mode use due to a UADE as described above,  
1067     closed-loop system use will be suspended if there are three or more cases of severe  
1068     hypoglycemia or three or more cases of hyperglycemia/ketotic events qualifying as SAEs across  
1069     the entire study in participants who have initiated Control-IQ technology use.

1070     Study activities could be similarly suspended if the manufacturer of any constituent study device  
1071     requires stoppage of device use for safety reasons (e.g. product recall). The affected study  
1072     activities may resume if the underlying problem can be corrected by a protocol or system  
1073     modification that will not invalidate the results obtained prior to suspension.

1074

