817 unaware that a use error has occurred. An unexpected physiological response of the patient is not

818 by itself considered a use error. A malfunction of a medical device that causes an unexpected  
819 result is not considered a use error. (ISO 14155:2020)

820

821 **7.2.2 Reportable Adverse Events**

822 For this protocol, a reportable adverse event includes any untoward medical occurrence that  
823 meets one of the following criteria:

- 824 1. An SAE as defined in section 7.2.1
- 825 2. An ADE as defined in section 7.2.1, unless excluded from reporting in section 7.3
- 826 3. An AE as defined in 7.2.1 occurring in association with a study procedure
- 827 4. An AE as defined in 7.2.1 not related to a device issue which leads to temporary or  
828 permanent discontinuation of a study device
- 829 5. An AE as defined in 7.2.1 that affects the participant's ability to complete any study  
830 procedures
- 831 6. An AE as defined in 7.2.1 for which a visit is made to a hospital emergency department
- 832 7. Hypoglycemia meeting the definition of reportable hypoglycemia as defined below
- 833 8. Diabetic ketoacidosis (DKA) or hyperosmolar hyperglycemic syndrome (HHS) as defined  
834 below; or in the absence of DKA/HHS, hyperglycemia or ketosis event meeting the criteria  
835 defined below.

836 Hypoglycemia and hyperglycemia not meeting the criteria below will not be recorded as adverse  
837 events unless associated with an Adverse Device Effect or discontinuation of the study device.  
838 Skin reactions from sensor placement are only reportable if severe and/or required treatment.

839 All reportable AEs—whether volunteered by the participant, discovered by study personnel  
840 during questioning, or detected through physical examination, laboratory test, or other means—  
841 will be reported on an AE form online. Each AE form is reviewed by the Medical Monitor to  
842 assess safety and to verify the coding and the reporting that is required.

843 **7.2.3 Hypoglycemic Events**

844 Hypoglycemia not associated with an Adverse Device Effect or discontinuation of the study  
845 device is only reportable as an adverse event when one of the following criteria is met:

- 846 • a hypoglycemic event occurred meeting the following definition of severe hypoglycemia:  
847 the event required assistance of another person due to altered consciousness, and required  
848 another person to actively administer carbohydrate, glucagon, or other resuscitative  

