874                   involving hyperglycemia or ketosis, or the participant contacted the site and received  
875                   guidance on how to manage the hyperglycemia/ketosis

876                   Hyperglycemic events are classified as DKA if the following are present:

877                   • Symptoms such as polyuria, polydipsia, nausea, or vomiting;

878                   • Serum ketones  $>1.5$  mmol/L or large/moderate urine ketones;

879                   • Either arterial blood pH  $<7.30$  or venous pH  $<7.24$  or serum bicarbonate (or CO2)  $<15$ ; and

880                   • Treatment provided in a health care facility

881                   Hyperglycemic events are classified as HHS if the following are present:

882                   • Symptoms such as polyuria, polydipsia, nausea, or vomiting;

883                   • Plasma glucose levels are very elevated (typically  $>600$  mg/dL);

884                   • Plasma effective osmolarity is  $>320$  mOsm/L;

885                   • Absence of significant ketones; and

886                   • Treatment provided in a health care facility

887                   When a hyperglycemia/ketotic event qualifies as an SAE as defined in section 7.2.1 , a  
888                   Hyperglycemia/DKA Form should be completed in addition to the Adverse Event Form. Events  
889                   meeting DKA or HHS criteria should be considered to be serious adverse events with respect to  
890                   reporting requirements. Hyperglycemia events not meeting criteria for DKA or HHS generally

891 will not be considered as serious adverse events unless one of the SAE criteria in section 7.2.1 is  
892 met.

893 When a hyperglycemia/DKA event occurs during use of a study device, it generally will be  
894 considered to be unrelated to the device (per section 7.2.5) if the device functioned as intended  
895 and there does not appear to be a flaw in how the device is intended to function.

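### Protocol 7.6.1 and 7.5 omit HHS from the safeguards that follow a first DKA or severe hypoglycemia: the condition for continuing, and notice to the Clinical Study Director

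*Protocol*

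**What the plan says.** Protocol 7.6.1 lists the reasons for discontinuing a participant when no device malfunction is involved. One is a count: "Two distinct episodes of DKA, HHS, or severe hypoglycemia as defined above, so only a" second event of any of these types is tolerated before participation stops. HHS is named there.

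Two paragraphs on single events follow, and neither names HHS:

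- The review of cause and attribution to the device: "Each DKA or severe hypoglycemia event will be reviewed by the Medical Monitor with respect" to these questions.
- The condition for continuing: "An additional requirement for continued study participation following a single DKA or severe" hypoglycemia event. The site investigator must judge that the event can be explained, is not expected to happen again, and leaves further use of the system safe. The Medical Monitor must agree. If the Monitor decides that further use is unsafe, the participant is discontinued.

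Section 7.5 has a matching sentence on information flow: "The Clinical Study Director will be informed of all cases of severe hypoglycemia and DKA", and also of every reported device issue.

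Elsewhere the protocol puts HHS on the same footing as DKA. Section 7.2.2 makes both reportable ("Diabetic ketoacidosis (DKA) or hyperosmolar hyperglycemic syndrome (HHS) as defined" in the protocol). Section 7.2.4 makes both serious, saying that events "meeting DKA or HHS criteria should be considered to be serious adverse events with respect to" reporting.

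**The concern.** HHS counts towards discontinuation at the second episode, but the first episode does not trigger the check that a first DKA triggers. No reason is given for the difference.

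The population makes the omission awkward. Everyone enrolled has type 2 diabetes. Protocol 1.4.1.3 says DKA is less common in type 2 than in type 1 diabetes, and it names HHS as a risk of extreme hyperglycemia with dehydration. The protocol summary lists the two together as a key safety endpoint.

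What is at stake is the handling of individual participants. A site that follows 7.6.1 to the letter could let someone go on with closed-loop use after a first HHS event with no second opinion required. Endpoints and analyses are not affected.

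**Working it through.** The plan gives no figure to reproduce. The check compares the provisions and then works out when the count rules act.

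**Step 1. Which provisions reach HHS**

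| Provision | Severe hypoglycemia | DKA | HHS |
|---|---|---|---|
| Protocol summary, key safety endpoints | named | named | named |
| 7.2.2 reportable adverse event | named | named | named |
| 7.2.3 and 7.2.4, treated as an SAE | named | named | named |
| 7.5 Medical Monitor review of all reported events | covered | covered | covered |
| 7.5 Director informed of every case | named | named | **absent** |
| 7.6.1 suspension after a malfunction | named | named | absent |
| 7.6.1 two-episode rule | named | named | named |
| 7.6.1 review of cause for each event | named | named | **absent** |
| 7.6.1 condition for continuing after one event | named | named | **absent** |
| 7.6.2 study-level suspension | named | covered as an SAE | covered as an SAE |
| SAP 13 review as events occur | named | named | only if a device-related SAE or a UADE |

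**Step 2. Whether DKA could be read to include HHS.** It could not. Under 7.2.4, DKA needs serum ketones above 1.5 mmol/L or large or moderate urine ketones, together with a low pH or bicarbonate. HHS needs significant ketones to be absent. The two-episode rule also lists them as separate events.

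**Step 3. Whether another provision supplies the missing condition**

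- 7.5 provides that "The study Medical Monitor will review all adverse events and adverse device events that are" reported, with SAEs typically seen within 24 hours. Section 7.2.5 adds a causality assessment. Both are reviews, and neither makes continuation depend on the Monitor's agreement.
- 7.6.1 requires discontinuation if the investigator thinks continuing is unsafe. That covers the safety element. It does not ask whether the event is explained or likely to recur, and nobody else has to agree.
- The duty to discontinue on the Monitor's determination sits inside the paragraph on a single DKA or severe hypoglycemia event, so it refers to those events.
- SAP 13 lets the Monitor or sponsor ask for protocol changes, suspension or stoppage. That acts on the study, not on one participant's continuation.

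**Step 4. When the count rules act**

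- Within a participant, 7.6.1 acts at 2 episodes, so 2 − 1 = 1 HHS event can pass.
- Across the study, 7.6.2 acts at 3 hyperglycemic or ketotic SAEs, so 3 − 1 = 2 can pass.
- With no other such SAE, up to 2 participants could each have one HHS event and neither rule would act.

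**Step 5. The route to the Director.** A device-related HHS event goes on a device issue form under 7.3, and 7.5 sends all reported device issues to the Director. But 7.2.4 says hyperglycemia events are generally classed as unrelated when the device worked as intended, so this route would often not apply. A DKA case reaches the Director whatever its attribution.

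**Step 6. Places where the omission has little effect.** The cause-review sentence in 7.6.1 is largely duplicated for HHS by the general review in 7.5 and the causality assessment in 7.2.5. The malfunction sentence ("In the case of an unanticipated system malfunction resulting in a severe hypoglycemia or DKA" event) also covers malfunctions that could have led to either outcome, and the UADE provisions apply as well. SAP 13 has reportable adverse events reviewed periodically, and Protocol 7.5 already covers every reported event.

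**The case against.** The strongest reply is that this is a drafting slip with little practical effect. An HHS event is an SAE, the Medical Monitor will normally see it within a day and assess causality, and the investigator must already stop anyone thought unsafe. The DKA paragraph sets no pause in device use and no deadline for agreement, so the real difference is one formal step. The Director has no decision power in the visible text, and under SAP 13 the sponsor periodically sees reportable adverse events, HHS among them. Exposure is up to 30 people for six weeks, and HHS may never occur. The figure of two participants comes only from the thresholds and would apply equally to DKA.

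Most of this stands, and it is why the point is minor. The safety element of the investigator finding is largely covered already, the Director gap concerns information only, and the count in Step 4 says nothing about how likely an event is. None of it supplies what is missing: a finding that the event is explained and unlikely to recur, and the Monitor's agreement as a condition of continuing.

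**Conclusion.** The concern holds. Protocol 7.6.1 is internally inconsistent as written, and the severity is minor. There are two functional gaps: the condition for continuing after a single event, and notice to the Director. The other three places (the cause-review sentence, the malfunction sentence and SAP 13) are matters of consistent wording.

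The conclusion rests on a literal reading of 7.6.1 and 7.5 and on the separate definitions in 7.2.4. It assumes nothing about how often HHS occurs, and the documents give no rate. A careful Medical Monitor might well step in after a first HHS event, but the text does not make continuation depend on it.

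**What to change.** Add HHS to these sentences:

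1. Protocol 7.6.1, review of cause: begin with *Each DKA, HHS, or severe hypoglycemia event*.
2. Protocol 7.6.1, condition for continuing: *a single DKA, HHS, or severe hypoglycemia event*.
3. Protocol 7.5, Director sentence: *severe hypoglycemia, DKA, and HHS*.
4. For consistency, the malfunction sentence in Protocol 7.6.1 and the Medical Monitor's list in SAP 13.

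This changes wording in four protocol sentences and one SAP sentence. Endpoints, visits, sample size and analyses stay as they are. Protocol 11.2 requires IRB approval before any amendment is implemented, so the change could travel with the next amendment. The study is meant to inform a larger one, and correcting the text also keeps the gap from being carried forward if the wording is reused.

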## 1075                   **Chapter 8: Miscellaneous Considerations**

### 1076                   **8.1 Drugs Used as Part of the Protocol**

1077 Participants will use either lispro or aspart insulin prescribed by their personal physician.  
1078 Participants not using lispro or aspart insulin at the time of screening may not start use of the  
1079 study device until they have one of these insulins available to them for use.

### 1080                   **8.2 Collection of Medical Conditions and Medications**

1081 Pre-Existing Condition: Any medical condition that is either present at screening, a chronic  
1082 disease, or a prior condition that could impact the participant's health during the course of the  
1083 study (e.g., prior myocardial infarction or stroke).

1084 *Medical Conditions during the study:* In addition to conditions meeting the reporting  
1085 requirements for an adverse event or device issue as described above, the following medical  
1086 conditions should also be reported: (1) new diagnosis of a chronic disease (i.e., not present at the  
1087 time of enrollment), and (2) any medical condition that could affect the participant's ability to  
1088 carry out any aspect of the protocol or could affect an outcome assessment.

1089 *Medications:* All medication for the treatment of chronic pre-existing conditions, medical  
1090 conditions (including medical conditions that do not require recording), and/or adverse events  
1091 that the participant is currently taking at screening and during the course of the study should be  
1092 recorded. Nutraceuticals and preventative treatment also should be recorded. Medications only  
1093 taken as needed either can be recorded when prescribed or only recorded if used during the  
1094 study. Glucagon for treatment of severe hypoglycemia will only be recorded if used during the  
1095 study.

### 1096                   **8.3 Prohibited Medications, Devices, Treatments, and Procedures**

1097 Participants using other insulins at the time of enrollment will be asked to contact their personal  
1098 physician to change their prescribed personal insulin to lispro or aspart for the duration of the  
1099 trial.

1100 AfreZZa (inhaled insulin) or concurrent use of basal insulins will not be permitted during device  
1101 use in the trial. Additional medications to treat glycemia (such as SGL-2 inhibitors or GLP-1  
1102 receptor agonists), commonly used by individuals with type 2 diabetes concurrently with insulin  
1103 use, will be allowed if the participant is on a stable dose of such medication for the last 3 months.  
1104 Sulfonylurea use and meglitinide use will not be allowed during the trial.

1105 No new additional glucose lowering medications may be added during the trial.

1106 Medications used for weight loss will be allowed if the participant is on a stable dose of such  
1107 medication for the last 3 months. No new medications for weight loss may be added during the  
1108 trial.

1109 Additional medications may be excluded per judgement of the investigator.

1110 The investigational study devices (study insulin pump, study CGM system) must be removed  
1111 before Magnetic Resonance Imaging (MRI), Computed Tomography (CT) or diathermy treatment.  
1112 Participants may continue in the trial after temporarily discontinuing use if requiring one of the  
1113 treatments above.

1114                   **8.4 Precautionary Medications, Treatments, and Procedures**

1115   Not applicable.

1116                   **8.5 Prophylactic Medications, Treatments, and Procedures**

1117   Not applicable.

1118                   **8.6 Rescue Medications, Treatments, and Procedures**

1119   All participants will be required to have a commercially available glucagon (or glucagon analog)  
1120   preparation for treatment as needed of severe hypoglycemia.

1121                   **8.7 Pregnancy Reporting**

1122   If pregnancy occurs, the participant will be discontinued from the study. The occurrence of  
1123   pregnancy will be reported to the Coordinating Center within seven days and to the JCHR IRB as  
1124   an Unanticipated Problem within seven calendar days.

1125                   **8.8 Participant Compensation**

1126   Participant compensation will be specified in the informed consent form.

1127                   **8.9 Participant Withdrawal**

1128   Participation in the study is voluntary, and a participant may withdraw at any time. For  
1129   participants who withdraw, their data will be used up until the time of withdrawal.

1130                   **8.10 Confidentiality**

1131   For security and confidentiality purposes, participants will be assigned an identifier that will be  
1132   used instead of their name. Protected health information gathered for this study will be shared  
1133   with the coordinating center, the Jaeb Center for Health Research in Tampa, FL. De-identified  
1134   participant information may also be provided to research sites involved in the study.

